9.4.1.3 Adverse Event's Severity

The following classification should be used.

Adverse events intensity or severity should be classified as follows:

- ✚ **Mild.** They occur with easily tolerated signs and symptoms. They do not require treatment or extend hospitalization, and do not necessarily require drug's discontinuation.
- ✚ **Moderate.** They interfere with usual activities (may cause work or school absenteeism) without affecting patient's life directly. They require pharmacological therapy and do not necessarily require the discontinuation of the drug which caused the event, reaction, or suspect adverse reaction.
- ✚ **Severe.** They interfere with usual activities (may cause work or school absenteeism). They require pharmacological therapy and the discontinuation of the drug which caused the event, reaction, or suspect reaction.

9.4.1.4 Laboratory Abnormal Findings and other Abnormal Findings throughout the Study

Abnormal laboratory findings and other abnormal findings during the study (e.g., ECG trace) should not reported as serious adverse events, unless they are related to clinical signs and symptoms, which cause treatment's discontinuation or, in the other hand, they are considered clinically important by the Principal Investigator. In the event laboratory abnormality meets these criteria, identified medical condition (for instance, anemia, and high ALT) should be reported as an adverse event instead of the abnormal value by itself.

9.4.1.5 Unexpected Adverse Event

An unexpected adverse event is any adverse event which specificity or severity are not foreseen in the most recent product's information (Investigator's Brochure - or package insert for marketed products). Likewise, reports which provide important information about specificity or severity of a known adverse event, already documented, constitute unexpected adverse events. For instance, any event more specific or more severe than those described in the Investigator's Brochure should be considered "unexpected".

9.4.1.6 Serious Adverse Event

A serious adverse event is any unexpected medical occurrence which at any dose:

- ✚ Results in death.
- ✚ It is life-threatening.
- ✚ Requires hospitalization or prolongs the existing hospitalization.
- ✚ Results in persistent or important disability or incapacity.
- ✚ It is a congenital abnormality or birth defect.
- ✚ It is clinically important event.

Some clinically important events, although they do not lead to death, are not life-threatening or require hospitalization, may be considered serious adverse events based on the appropriate medical judgment and the need of medical or surgical care to avoid the events previously mentioned in this definition. Examples of those medical events include: allergic bronchospasm which require intensive care in the emergency room or at home, blood dyscrasias or seizures which require hospitalization, or the development of drug's dependence or abuse.

Life-threatening means that the subject was in danger, as per Investigator's judgment, immediate risk of death due to the reaction when it occurred.

9.4.1.7 Adverse Event of Special Interest

Hypoglycemia is a condition characterized by abnormally low blood glucose (blood sugar) levels, usually less than 70 mg/dl and may be associated with the following symptoms: headache, increase appetite, nausea, vomit, tiredness, drowsiness, sleep disorders, restlessness, aggressiveness, reduced concentration, wakefulness and reaction; depression, confusion; visual and speech disorders; aphasia; tremors, paresis, sensory disorders, dizziness, helplessness feeling, lack of self-control, delirium, seizures, shallow breathing, bradycardia, drowsiness, syncope which might lead to coma and death. Subjects will be monitored closely.

In the event of a non-serious AESI, the investigator will complete the AESI Report Form and send it to the Sponsor. Names, addresses, and telephone and fax numbers for AESI reporting will be included on the Report Form. Serious AESIs have to be reported in an expedited manner as SAEs as outlined above.

9.4.1.8 Recording Methods and Adverse Events Assessment

Any adverse event occurring during the study period should be recorded in the medical chart as well as in the case report form for each subject.

Documentation should be supported by a record into the subject's medical chart. Any abnormality in laboratory tests, considered clinically relevant, for instance, those which lead to the subject's withdrawal from the study, require treatment, cause evident clinical onset in the subject, considered relevant by the Investigator, should be reported as an adverse event. All adverse events should be described in details, including subject's identity (name, age and gender), adverse event, suspected drug, reporter's data, onset and end date for the event, event's name and treatment, generic and brand name, dosage, route of administration, reason of prescription, event's consequences and relevant data in the medical history.

9.4.1.9 Definition of Reporting Period for Adverse Events

Report of adverse events will start as per the informed consent form signature and until and continues through the trial tart as per the informed consent form signature and until end-of-trial examination (last contact with the subject).

9.4.1.10 Procedure for Reporting Adverse Events and Serious Adverse Events

Report of adverse events will be the responsibility of the PPD [REDACTED] and it will be made according to the ICH GCP and the standard operating procedure, code: PPD [REDACTED] REPORT OF CLINICAL AND BIOAVAILABILITY STUDIES ADVERSE EVENTS

In the event of any new SAE occurring during the reporting period, the Investigator must immediately (within a maximum of 24 HOURS after becoming aware of the event) inform the Sponsor or its designee in writing. All written reports should be transmitted using the SAE Report Form, which must be completed by the Investigator following specific completion instructions.

In exceptional circumstances, an SAE (or follow-up information) may be reported by telephone; in these cases, a written report must be sent immediately thereafter by fax or e-mail. Names, addresses, and telephone and fax numbers for SAE reporting will be included in the trial-specific SAE Report Form.

Relevant pages from the CRF may be provided in parallel (for example, medical history, concomitant drugs). Additional documents may be provided by the Investigator, if available (for example, laboratory results, hospital report, autopsy report). In all cases, the information provided on the SAE Report Form must be consistent with the data about the event recorded in the CRF.

The Investigator must respond to any request for follow-up information (for example, additional information, outcome, final evaluation, other records where needed) or to any question the Sponsor/designee may have on the AE within the same timelines as those noted above for initial reports. This is necessary to ensure prompt assessment of the event by the Sponsor or designee and (as applicable) to allow the Sponsor to meet strict regulatory timelines associated with expedited safety reporting obligations.

Requests for follow-up will usually be made via the responsible Monitor, although in exceptional circumstances the Global Drug Safety department may contact the Investigator directly to obtain further information or to discuss the event.

Report of adverse events will be made according to the ICH GCP and the standard operating procedure, code: PPD [REDACTED] REPORT OF CLINICAL AND BIOAVAILABILITY STUDIES ADVERSE EVENTS and the Mexican Official Standard for the Setting-up and Operations of Pharmacovigilance in Mexico, NOM-220-SA1-2012. Therefore, any serious adverse event or suspect serious adverse reaction should be notified to the National Center of Pharmacovigilance (CNFV) from the Federal Commission for the Protection Against Sanitary Risks (COFEPRIS) as well as to the Sponsor within the first 24 h following the Investigator is aware of it. A supplemental report, as detailed as possible and including all information collected, should be sent within 15 days. Report to the CNFV will be made by the Pharmacovigilance Officer at the PPD [REDACTED] [REDACTED]. To comply with NOM-220-SSA1-2012, mild or moderate, expected and unexpected adverse reactions should be reported by the study Principal Investigator at the PPD [REDACTED] [REDACTED], along with the clinical stage report to the CNFV.

PPD [REDACTED]
[REDACTED]
[REDACTED] [REDACTED]
[REDACTED]

The reports to Merck shall be sent in English using the Merck SAE form via fax or email within 24 hours.

PPD [REDACTED]

9.4.1.11 Report of Safety Information to the Health Authorities, Ethics and Investigation Committee and Investigational Committee

According to local law and regulation, all serious and non-serious adverse events should be reported to the appropriate Ethics and Investigation Committee, Investigational Committee and to the Health Authorities. This will be carried out according to the ICH GCP and the standard operating procedure, code: PPD [REDACTED] Report of clinical and bioavailability studies adverse events

The Investigator must comply with any applicable site-specific requirements related to the reporting of SAEs (particularly deaths) involving trial subjects to the IEC/IRB that approved the trial.

In accordance with ICH GCP, the Sponsor/designee will inform the Investigator of “findings that could adversely affect the safety of subjects, impact the conduct of the trial or alter the IEC’s/IRB’s approval/favorable opinion to continue the trial.” In particular and in line with respective regulations, the Sponsor/designee will inform the Investigator of AEs that are both serious and unexpected and are considered to be related to the administered product (“suspected unexpected serious adverse reactions” or SUSARs). The Investigator should place copies of Safety Reports in the Investigator Site File. National regulations with regard to Safety Report notifications to Investigators will be taken into account.

9.4.1.12 Monitoring of Subjects with Adverse Events

Adverse events are recorded and assessed on an ongoing basis throughout the study, and they will be assessed for the final outcome in the 14-day follow-up following the last dose of the drug. All ongoing adverse events, including the follow-up period, should be watched and followed-up by the Investigator until they are stable or until their outcome is known; unless it is documented that the subject is "lost to follow-up". All reasonable efforts should be made to collect information and these should be documented. It is also the Principal Investigator's responsibility to ensure that all additional and necessary therapeutic measures are taken as well as the follow-up procedures.

9.4.2 Pregnancy and Exposure to Drugs in the Uterus

All pregnancies, with a conception date estimated during the period defined in section 9.5.1.3. will be recorded as AE in the appropriate CRF page/section. For female subjects and male subjects' female partners as AE or SAE depending on the outcome of the pregnancy. The Principal Investigator should inform immediately the Sponsor or designated person about any pregnancy using a Pregnancy Report Form which should be submitted according to the same procedure for SAE referred in section 9.4.1.10.

The Principal Investigator or designated person should follow-up, document and report all pregnancies outcomes, even if subjects were withdrawn from the study.

The Principal Investigator should inform the Sponsor or designated person about the outcome using the Pregnancy Report Form. In case of an abnormal outcome, the SAE Report Form will be used. In case subject, child/fetus experienced an event, the Parent-Child/Fetus Adverse Event Report Form will be used.

Any abnormal outcome should be reported immediately as described in section 8.4.1.4. All abnormal outcomes should be reported (the observation period comprises 45 days following the delivery).

In case of pregnancy during the study, the subject should be withdrawn and no further IMP has to be given. Sponsor or designated person should be immediately informed and follow-up should be made as aforementioned.

Uncontrolled diabetes during pregnancy (gestational or permanent) is associated with increased congenital abnormalities and perinatal mortality. The use of the combination drug Metformin and Gliclazide has not been studied in pregnant women.

A limited amount of data from the use of Metformin in pregnant women does not indicate an increased risk of congenital abnormalities. Animal studies with Metformin do not indicate harmful effects with respect to pregnancy, embryonic or fetal development, parturition or postnatal development.

With Gliclazide no teratogenic effects have been shown in animal studies, but lower fetal body weight was observed in animals receiving doses 25 fold higher than the maximum recommended dose in humans. No impairment of fertility was seen in a study with male and female rats.

When the patient plans to become pregnant and during pregnancy, it is recommended that diabetes is not treated with Gliclazide, but insulin should be used to maintain blood glucose levels as close to normal as possible.

Pregnancy occurring during a patient's participation in a clinical trial, although not typically considered an SAE, must be notified to the sponsor within the same timelines as an SAE (within one working day) on a Pregnancy Monitoring Form. The outcome of a pregnancy should be followed up carefully and any abnormal outcome of the mother or the child should be reported. This also applies to pregnancies following the administration of the investigational product to the father prior to sexual intercourse.

Based on the outcome and the timing of the delivery, the pregnancies during the clinical trial can be categorized into the followings:

Female is study participant and becomes pregnant during study participation:

1. Normal outcome before end of study
2. Abnormal outcome before end of study
3. Normal outcome after end of study
4. Abnormal outcome after end of study

Female is partner of study participation and becomes pregnant during study:

5. Normal outcome before or after end of study
6. Abnormal outcome before or after end of study

In all of these situations, the Pregnancy Monitoring Form should always be filled out. However, only for situation #2, a SAE needs to be reported.

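### Protocol Section 9.4.2 gives two incompatible rules on when an abnormal pregnancy outcome is reported as an SAE; under the narrower rule no birth outcome would qualify

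*Protocol*

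**What the plan says.** Both rules stand in the current text of Protocol Section 9.4.2.

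The first part says of pregnancy outcomes: "In case of an abnormal outcome, the SAE Report Form will be used". It sets no time limit. It classes pregnancies of participants and of male subjects' partners as AE or SAE according to outcome, and it extends observation of abnormal outcomes to 45 days after delivery.

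The second part sorts pregnancies into six situations. Three have an abnormal outcome:

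- for a female participant, "2. Abnormal outcome before end of study" and "4. Abnormal outcome after end of study";
- for a male participant's partner, "6. Abnormal outcome before or after end of study".

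A Pregnancy Monitoring Form is required in all six situations, and abnormal outcomes of mother or child are to be reported. The list then closes: "However, only for situation #2, a SAE needs to be reported".

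Other sections bear on the point:

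- Section 9.4.1.6 includes among the criteria for seriousness: "It is a congenital abnormality or birth defect".
- Section 9.4.1.9 ends the adverse event reporting period at the end-of-trial examination. Section 9.4.1.10 asks for SAEs that occur in that period, "within a maximum of 24 HOURS after becoming aware of the event".
- Section 9.4.2 says that a pregnancy "must be notified to the sponsor within the same timelines as an SAE (within one working day").
- Section 7.7 places the end of the trial at the last contact with the last subject.

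The SAP does not address pregnancy; its Section 18 refers to the clinical report.

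**The concern.** For situations 4 and 6 the two parts of Section 9.4.2 give opposite instructions, and an investigator cannot follow both. SAE status matters because it triggers the 24-hour notice to the sponsor and to the national pharmacovigilance centre under Section 9.4.1.10.

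The cases in dispute are also the main ones. The trial is short compared with a pregnancy, so the outcomes of most concern after exposure, those seen at birth, come after the trial has closed. The narrower rule would keep all of them off the SAE form, although the protocol's own seriousness criteria name such outcomes. The same section says that the combination has not been studied in pregnant women.

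**Working it through.** **Step 1. The two rules side by side, for the abnormal outcomes only**

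| Situation | First part of 9.4.2 | Closing sentence of 9.4.2 |
|---|---|---|
| 2: participant, before end of study | SAE form | SAE |
| 4: participant, after end of study | SAE form | not an SAE report |
| 6: partner, at any time | SAE form | not an SAE report |

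The rules agree on one situation of three.

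**Step 2. Reproduce the plan's durations (Protocol Section 1)**

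- Per subject: 30 + 3 × 14 + 8 = 80 days, as stated.
- Whole study: 8 + 8 + 2 = 18 weeks, as stated; 18 × 7 = 126 days.

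**Step 3. How long can a pregnancy run before end of study?**

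The last period starts 42 days after the first (Section 9.2.7).

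- First dose to the 168-hour sample: 42 + 7 = 49 days.
- First dose to the 8-day end of study: 42 + 8 = 50 days.
- First dose to the end of the 14-day follow-up (Section 9.4.1.12): 42 + 14 = 56 days.
- Conduct phase plus follow-up: (8 + 2) × 7 = 70 days.
- Whole study including screening: 126 days.

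Situations 1 to 4 turn on the end of the study, not on one subject's last sample, so 49 days is not the relevant limit. The most generous limit is 126 days, which allows for conception on the first day of screening. Section 8.4 has all 40 subjects dosed on the same mornings, so for a pregnancy exposed to study drug the realistic span is nearer 50 to 70 days.

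**Step 4. Compare with time to birth**

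The documents do not give a length of gestation. Assume birth between 24 and 40 gestational weeks, counted from 2 weeks before conception:

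- days from conception to birth = (gestational weeks − 2) × 7;
- 24 weeks: 22 × 7 = 154 days;
- 40 weeks: 38 × 7 = 266 days.

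Even the most generous limit falls short of the earliest birth by 154 − 126 = 28 days. Against 70 days the shortfall is 154 − 70 = 84 days.

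**Step 5. Consequence**

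Under the closing sentence, situation 2 can hold an early loss or a termination but no birth. The observation to 45 days after delivery, set in the first part, could then never lead to an SAE report.

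**The case against.** The strongest reply is that nothing goes unreported. The second part of Section 9.4.2 requires the Pregnancy Monitoring Form every time and asks for abnormal outcomes to be reported, including after paternal exposure. The first part adds a parent-child/fetus form. This stands. A reader might infer that a birth defect after exposure would go unreported, and the documents do not support that. What differs is the SAE classification and the form.

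A second reply is that the narrower rule has a rationale. Section 9.4.1.6 defines what is serious but sets no reporting window. Sections 9.4.1.9 and 9.4.1.10 tie SAE reports to a period that closes at the end-of-trial examination. Situation 4 falls after that period, and situation 6 concerns someone who is not a participant. This also stands in part. A reader might infer that the closing sentence plainly breaches the protocol's SAE definition, but these sections make that conflict less direct. They do not remove the conflict inside Section 9.4.2, whose first part covers partners and runs past delivery.

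Third, the one-working-day wording is a parenthesis in a sentence that defers to the SAE timeline, so the difference from 24 hours is secondary. It is still real over a weekend: one working day from Friday runs to Monday.

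Last, pregnancies should be few. Twenty women are planned, highly effective contraception is required, and a negative test is needed before each period. This limits the size of the problem but does not settle which rule applies.

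**Conclusion.** The contradiction is established from the text of Section 9.4.2, and no other section resolves it for situations 4 and 6. Under the narrower rule no birth outcome of a pregnancy begun in the study would be an SAE. That conclusion rests on the study lasting about 18 weeks as planned and on the assumed range of 24 to 40 gestational weeks. The margin is 28 days at the extreme and wider for exposed pregnancies.

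The practical size is small: few pregnancies are expected, abnormal outcomes still reach the sponsor on another form, and no pharmacokinetic endpoint or bioequivalence conclusion is touched. The documents do not show which rule was intended. It is a minor but definite inconsistency in safety reporting, and worth correcting because the correction is so cheap.

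**What to change.** Reconcile the two parts of Section 9.4.2 with each other and with Sections 9.4.1.6, 9.4.1.9 and 9.4.1.10. The result should be one rule that says, for each of situations 2, 4 and 6, whether the SAE form is used and whether that duty continues after the end-of-trial examination. State one deadline, so that the working-day wording and the 24-hour wording agree.

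In the same edit, correct two cross-references in Section 9.4.2, to 8.4.1.4 and 9.5.1.3, since neither section exists in the protocol. Also settle whether the Pregnancy Report Form and the Pregnancy Monitoring Form are the same document.

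The cost is one or two sentences of protocol text. Sample size, procedures and analysis do not change.

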9.4.3 Clinical Laboratory Assessments

Blood samples for hematology:

1. Two (2) blood samples will be collected per period at times established in the schedule. Test tubes with EDTA K2, specifically designed for venipuncture, will be used.
2. Each sample will be 4 mL. Blood withdrawn to clean catheter should be disposed prior to the blood sample collection (purge).
3. A \pm 1 minute window is allowed for sampling.
4. Samples should be maintained at room temperature (between 20 and 25 °C [68 °F to 77 °C]).
5. Blood tubes will be labelled with Study No. (##), Case No. (C##), Sample No. (S##) and Visit No. (V#) according to the SOP, code PPD [REDACTED] Pre organization for conducting a study of interchangeability and biocomparability; PPD [REDACTED] Processing and packaging of biological samples for studies interchangeability and biocomparability. They will be kept at room temperature until their delivery to the clinical laboratory.

Samples for blood chemistry and glucose determination:

1. Two (2) blood samples for blood chemistry and 5 samples for glucose determination will be collected per period at times established in the schedule and in test tubes without anticoagulant specifically designed for venipuncture.
2. Each sample will contain 6 mL for blood chemistry and 3 mL for glucose determination. Blood withdrawn to clean catheter should be disposed prior to the blood sample collection (purge).
3. A \pm 1 minute window is allowed for sampling.
4. Samples should be maintained at room temperature (between 20 and 25 °C [68 °F to 77 °C]).
5. Blood tubes will be labelled with Study No. (##), Case No. (C##), Sample No. (S##) and Visit No. (V#) according to the SOP, code, PPD [REDACTED] Pre organization for conducting a study of interchangeability and biocomparability; PPD [REDACTED] Processing and packaging of biological samples for studies interchangeability and biocomparability. They will be kept at room temperature until their delivery to the clinical laboratory.

Blood samples for coagulation:

1. Two (2) blood samples will be collected per period at times established in the schedule in test tubes with sodium citrate specifically designed for venipuncture.
2. Each sample will be 3 mL. Blood withdrawn to clean catheter should be disposed prior to the blood sample collection (purge).
3. A \pm 1 minute window is allowed for sampling.
4. Samples should be maintained at room temperature (between 20 and 25 °C [68 °F to 77 °C]).
5. Blood tubes will be labelled with Study No. (##), Case No. (C##), Sample No. (S##) and Visit No. (V#) according to the SOP, code, PPD [REDACTED] Pre organization for conducting a study of interchangeability and biocomparability; PPD [REDACTED] Processing and packaging of biological samples for studies interchangeability and biocomparability They will be kept at room temperature until their delivery to the clinical laboratory.

Urine samples for urinalysis/ microscopic analysis / sediment:

1. Two (2) urine samples will be collected per period at the times established in the schedule.
2. Samples should be maintained at room temperature (between 20 and 25 °C [68 °F to 77 °C]).
3. Urine containers will be labelled with Study No. (##), Case No. (C##), Sample No. (S##) and Visit No. (V#) and will be kept at room temperature until their delivery to the clinical laboratory.

Urine samples will be taken from fresh, spontaneous urine from each subject. The following parameters will be evaluated by Aution max 4280 Urine analyzer:

- ✚ pH, specific gravity
- ✚ Proteins*, glucose, ketones, nitrites*, bilirubine, urobilinogen, blood*, leucocytes*
- ✚ * if positive, a microscopic examination (urine sediment) will be performed.
- ✚ Urine sample from these subjects should be kept in the fridge.

Containers will be labeled with Study No. (##), Case No. (C##), Sample No. (S##) and Visit No. (V#) according to the SOP, code, PPD [REDACTED] Sampling for clinical laboratory for subjects' screening in interchangeability and biocomparability studies. They will be kept in the fridge until their delivery to the clinical laboratory.

▪ **Pregnancy test:**

For all women of childbearing potential one blood sample per period will be collected for pregnancy tests (qualitative and quantitative) at day -1 of each treatment period in test tubes specifically designed for venipuncture without anticoagulant.

5 mL of blood will be collected and processed as follows:

- ✦ Each sample will be centrifuged at 2500 x g for 15 minutes at 4 °C [39.2 °F] (± 2 °C [35.6 °F]) to obtain at least 1 mL of plasma.
- ✦ Samples should be maintained at room temperature (between 20 and 25 °C [68 °F to 77 °C]).
- ✦ Blood tubes will be labeled with Study No. (##), Sample No. (S##) and Visit No. (V#) according to the SOP, code, PPD [REDACTED] Tubes labeling and distribution in racks; BE-PNO-009 Collection of multiple blood samples for interchangeability and biocomparability studies. They will be kept at room temperature until their delivery to the clinical laboratory.
- ✦ Pregnancy qualitative test will be performed in the clinical unit with the One Step HCG insta test trip (serum), for In-Vitro diagnostic.
- ✦ Pregnancy quantitative test will be performed in the clinical laboratory with the architect i 2000 analyzer by Chemiluminescence.

The Sponsor should receive a list of laboratory normal ranges before shipping the study drug. Any change to the study laboratory normal ranges should be submitted to the Sponsor.

